2.1.3. TEV-48574 and Inflammatory Bowel Disease

TEV-48574 is a highly potent, fully human immunoglobulin G (IgG) subclass 1 (lambda) monoclonal antibody (mAb) with a molecular weight of 146 kDa that targets TL1A, encoded by the TNF superfamily member 15 (*TNFSF15*) gene.

It is a neutralizing antibody that binds TL1A and inhibits its binding to its cognate signaling receptor, DR3, preventing activation of the DR3-signaling pathway. TEV-48574 also inhibits the binding of TL1A to decoy receptor 3 (DcR3), which is a natural antagonist of the TL1A-DR3 interaction. TEV-48574 preferentially inhibits the TL1A-DR3 interaction over the TL1A-DcR3 interaction.

In colitis animal models, TEV-48574 has shown anti-inflammatory and anti-fibrotic effects during nonclinical studies.

Based on the TL1A/DR3 signaling interactions and the potential effects of TL1A inhibition on inflammation, the intended indications for UC and CD with TEV-48574 are for the treatment of adult patients with moderately to severely active UC who have had an inadequate response, loss of response, or intolerance to either conventional therapy or a biologic agent and/or JAK inhibitor; and for the treatment of adult patients with moderately to severely active CD who have had an inadequate response, loss of response, or intolerance to either conventional therapy or a biologic agent.

2.1.4. Purpose of Current Study

Many patients with IBD do not respond, lose response, or are intolerant to currently available treatments for UC and CD. Furthermore, some of the available therapeutic agents for IBD have been associated with significant safety issues. The anti-TL1A activity of TEV-48574 may have an anti-inflammatory and anti-fibrotic effect in patients with IBD, leading to improvement of their disease conditions, while demonstrating an acceptable safety profile.

The purpose of the study is to determine the pharmacokinetics, efficacy, safety, and tolerability of 2 different doses of TEV-48574 subcutaneously (sc) administered every 2 weeks (Q2W) in adult patients with moderate to severe UC or CD.

2.2. Findings from Nonclinical and Clinical Studies

Brief summaries of nonclinical pharmacology, pharmacokinetics, and toxicology studies and clinical studies are provided in the following sections. More detailed information is provided in the Investigator's Brochure (IB).

2.2.1. Nonclinical Studies

A comprehensive set of in vitro and in vivo nonclinical studies was conducted to support TEV-48574 long-term therapeutic use in humans.

TEV-48574 bioavailability following a single sc administration was on average 93.0% in monkeys and 133.8% in rats (the higher than expected bioavailability observed in rats was possibly due to inter-animal variability and/or variability with the analytical method). A typical mAb pharmacokinetic profile was observed in monkeys; low volume of distribution indicating distribution is mainly limited to vasculature, no sex differences could be observed in exposure, and systemic exposure generally increased in a dose proportional manner. TEV-48574 displayed sc absorption with time to maximum observed serum drug concentration (t_{max}) of 48 hours followed by a gradual monophasic decline in serum levels and a terminal elimination half-life ($t_{1/2}$) ranging between 155 and 177 hours. In rats, 90% of the animals developed anti-drug antibodies (ADAs) along with reduced exposure, while ADA prevalence was less than 20% in the repeat-dose non-Good Laboratory Practice (GLP) study in cynomolgus monkeys, with no major drop in exposure when ADAs were present. As such, the cynomolgus monkey was considered the only relevant species for long-term safety studies.

The nonclinical safety program conducted with TEV-48574 consisted of a 6-week and a 6-month repeat-dose toxicity GLP study in the cynomolgus monkey. In addition to standard assessments, the 6-week study included cardiovascular and respiratory assessments and the 6-month study conducted in sexually mature animals included fertility assessments. These studies were preceded by single-dose pharmacokinetic and tolerability studies and 2-week dose range finding

(DRF) studies in rats and monkeys. In addition, in vitro tissue cross-reactivity (TCR) studies and cytokine release assays were conducted.

The nonclinical safety program revealed no safety concerns. In the repeat-dose sc toxicology studies, there were no TEV-48574-related clinical observations, changes in body weights, food consumption, ophthalmology, and clinical pathology (hematology, coagulation, clinical chemistry, and urinalysis) following repeated administrations of TEV-48574. There were no TEV-48574-related changes in the numbers of circulating T lymphocytes, B lymphocytes, natural killer cells, and monocytes. There were no organ weight, or macroscopic or microscopic changes that could be attributed to TEV-48574. No TEV-48574-related effects were noted on blood pressure, electrocardiography, and respiratory rate nor on fertility parameters (menstrual cycle, testicular volume, echogenicity, and semen analysis). As no safety signal was observed in the studies, the no observable adverse effect level (NOAEL) was concluded to be the highest doses tested in the repeat-dose studies; 50 mg/kg for the rat (2-week study) and 100 mg/kg for the monkey (6-month study).

Results obtained from in vitro TCR studies suggested that interactions of TEV-48574 with human tissues are unlikely. TEV-48574 is considered unlikely to induce a cytokine storm/cytokine syndrome as indicated by the low level of cytokine induction from human peripheral blood mononuclear cells in cytokine release assays.

2.2.2. Clinical Studies

2.2.2.1. Phase 1 Study (TV48574-SAD-10126)

Study TV48574-SAD-10126 was a first-in-human (FIH), Phase 1, randomized, double-blind, placebo-controlled, parallel-group study to determine the safety, tolerability, pharmacokinetics, and immunogenicity of TEV-48574 in the following groups:

- healthy volunteers (HV; single ascending dose [SAD] portion of the study: single sc administration of 1, 4, 12, 36, 90, 200, 400, and 1000 mg or placebo)
- patients with asthma (multiple ascending dose [MAD] portion of the study: repeat sc administrations (3 sc administrations: 200 mg Q2W, 800 mg [loading dose]/600 mg [maintenance dose] Q2W, and 2300 mg [loading dose]/1600 mg [maintenance dose] Q2W, or placebo)

Within each of the 8 dose cohorts in the SAD portion of the study, 8 healthy subjects were randomized to receive a single sc dose of TEV-48574 (6 subjects) or placebo (2 subjects). A total of 48 subjects received TEV-48574 and 16 subjects received placebo. In the MAD portion of the study, 36 patients with mild allergic asthma were assigned to 1 of 3 cohorts (12 patients per cohort). Within each cohort, the patients were randomly assigned to receive TEV-48574 (9 patients) or placebo (3 patients). A total of 27 patients received TEV-48574 and 9 patients received placebo. The study was completed (last patient completed) on 26 February 2019.

2.2.2.1.1. Pharmacokinetics

In the SAD portion of the study, single sc doses of TEV-48574 at 1, 4, 12, 36, 90, 200, 400, and 1000 mg were administered in HV. After 1- and 4-mg doses, all TEV-48574 serum concentrations were below the limit of quantitation.

The $t_{1/2}$ of TEV-48574 in the SAD portion was similar across the studied dose range; generally exceeding 6.5 days in all SAD cohorts (range: approximately 6.5 to 9.6 days). TEV-48574 peak serum concentrations were typically reached between 72 and 96 hours postdose. Thereafter, TEV-48574 was eliminated gradually in a monophasic manner. For apparent total body clearance after extravascular administration (CL/F), mean estimates were similar across the dose range. The apparent volume of distribution after extravascular administration (V_z/F) was also similar across the dose range (8.24 to 15.13 L), indicating that TEV-48574 was mostly confined to the circulatory system.

From 36 to 1000 mg, the increase in TEV-48574 exposure was greater than dose proportional. However, TEV-48574 half-life, CL/F, and V_z/F appeared similar across all SAD doses, which is suggestive of linear pharmacokinetics. Over the 200- to 1000-mg dose range, dose proportionality was observed. Therefore, the overall slightly greater than dose proportional results may be less relevant as only doses of 200 mg or greater were brought forward into the MAD portion.

The pharmacokinetics of TEV-48574 was further characterized in patients with mild allergic asthma in the MAD portion of the study. Consistent with the results of the SAD portion in HV, the pharmacokinetics of TEV-48574 in patients was characterized by slow absorption. The $t_{1/2}$ of TEV-48574 at steady state ranged from 8.3 to 8.7 days and was not impacted by dose level. Half-life estimates appear similar to those for the SAD portion of the study, generally exceeded approximately 6.5 days in all cohorts. For CL/F, mean estimates were similar across the dose range tested in the MAD portion and were similar to the CL/F observed in the SAD portion. The V_z/F was similar across the studied dose range in the MAD portion (11.79 to 21.06 L), indicating that TEV-48574 was mostly confined to the circulatory system, consistent with what was observed in SAD portion of the study.

Across the dose range tested in the MAD portion for single and multiple-dose administration, TEV-48574 peak (maximum observed drug concentration [C_{max}]) and total (area under the concentration-time curve over 1 dosing interval [AUC_{τ}]) systemic exposure increased with increasing dose. From 200 to 2300 mg on day 1 and from 200 to 1600 mg at steady state, the increase in TEV-48574 exposure was dose proportional, indicated by the 90% confidence interval (CI) for the estimated slope for C_{max} and AUC_{τ} including unity (1.0).

Without a loading dose, there was weak accumulation following the first dose in cohort 1 in the MAD portion of the study (approximately 47%). After the loading dose administered to cohort 2, there was also weak accumulation (approximately 32%), suggesting that the loading dose may have been too low to achieve steady state as rapidly as intended, whereas the loading dose used for cohort 3 achieved steady-state conditions after the loading dose administration. Steady state was reached after the second dose for all dose regimens.

2.2.2.1.2. Safety

No deaths, serious adverse events, protocol-defined adverse events of special interest (PDAESIs; severe hypersensitivity reactions or anaphylaxis), or withdrawals due to adverse events were reported during the study.

No adverse events consistent with immunosuppression (including opportunistic or unusual infections), cytopenias, or systemic reactions were reported, and no safety signal with

treatment-emergent ADA responses was observed. The nature and incidence of the adverse events were similar between doses and comparable with those for placebo. There were no dose-related trends and no clinically meaningful differences observed between the treatment groups for laboratory tests, vital signs, electrocardiograms (ECGs), and physical examination findings.

The safety data of Study TV48574-SAD-10126 do not suggest any adverse drug reactions associated with TEV-48574 treatment except for transient nonserious injection site findings.

2.2.2.1.3. Immunogenicity

A subject/patient was classified as having a treatment-emergent ADA response if either: 1) a subject had a positive sample at any of the postdose time points, but not at the predose time point, or 2) a subject had positive samples at predose time point and 1 or more postdose time points, with at least a 4-fold increase in titers postdose relative to the predose sample ADA titers. (Note: Treatment-emergent ADA status was based on titer, but all ADA results in this document are presented as \log_{10} titer.)

Of the 48 subjects who received TEV-48574 in the SAD portion of the study, 23 subjects (47.9%) were identified as having a treatment-emergent ADA response. Treatment-emergent ADA responses were not associated with a safety signal. Treatment-emergent ADA responses were also observed in the cohorts that did not have measurable serum concentrations of TEV-48574 (cohorts 1 and 2, 1 and 4 mg TEV-48574, respectively). All ADAs occurred at 200 mg or lower except for 1 patient who received 1000 mg developed 1 transient ADA (low titer) 43 days after the dose was administered, suggesting that there may be a trend toward immunological tolerance at higher doses.

Three of 27 patients who received TEV-48574 (11% of patients tested) in the MAD portion were identified as having a positive treatment-emergent ADA response. All 3 patients were in cohort 1 (200 mg). In these patients, the observed ADA \log_{10} titer ranged from 0.6 to 2.5. One patient had treatment-emergent ADA responses at multiple time points starting by day 15, while the other 2 patients were ADA positive only at the end-of-study (EOS) visit (day 92), approximately 7 weeks after the last dose.

For pharmacokinetics, the single evaluable treatment-emergent ADA positive patient had C_{max} and area under the serum drug concentration-time curve from time 0 to the time of the last measurable drug concentration (AUC_{0-t}) at steady state that were 86% and 93% lower, respectively, at day 15, and 82% and 97% lower, respectively, at day 29, when compared with geometric mean values of ADA negative patients. No treatment-emergent adverse events were reported for treatment-emergent ADA positive patients in the MAD portion of the study.

2.2.2.2. Phase 1 Study (TV48574-PK-10180)

Study TV48574-PK-10180 was a Phase 1 open-label, randomized, single-dose study to evaluate the pharmacokinetics, safety, immunogenicity, and tolerability of TEV-48574 in healthy Japanese and Caucasian subjects. There were 3 single dose cohorts. Healthy Japanese subjects were randomized to 1 of 2 dose levels of TEV-48574 (█ or █ in cohort 1 or assigned to a dose of █ TEV-48574 in cohort 2. Healthy Caucasian subjects were assigned to a dose of █ in cohort 3.

The pharmacokinetic profile of TEV-48574 in Japanese subjects (n=24) was similar to pharmacokinetic profile in Caucasian subjects (n=8) across the absorption, distribution, and elimination phases; pharmacokinetic parameters in Japanese subjects were comparable to Caucasian subjects in the [REDACTED] dose cohorts and consistent with pharmacokinetic parameters in Caucasian subjects obtained from the TV48574-SAD-10126 study. The safety profile was consistent with that seen in the previous TEV-48574 studies with no evidence of any dose-related trends in adverse events in Japanese cohorts or differences between the Japanese and Caucasian subjects in any safety measures.

2.2.2.3. Phase 2a Study (TV48574-AS-20031)

Study TV48574-AS-20031 was a Phase 2a, PoC, randomized, double-blind, placebo-controlled, parallel-group study to evaluate the efficacy and safety of TEV-48574 in adults with type 2 (T2)-low/non-T2 severe uncontrolled asthma. This population of asthmatics is characterized by having an endotype and phenotype characterized by low peripheral eosinophil counts; sputum that contains neutrophils or is paucigranulocytic; a history of relatively late-onset asthma symptoms; an increased association with obesity; and a relative resistance to topical, oral, and/or parenterally administered corticosteroids.

The study was initiated in Quarter 3 (Q3) of 2020. Approximately 124 to 174 patients (18 years of age and above) were planned to be enrolled, with the primary objective of the study to evaluate the effect of TEV-48574 compared with placebo on Loss of Asthma Control (LoAC). Patients were randomly assigned to receive a [REDACTED] of [REDACTED] and a maintenance dose of [REDACTED] TEV-48574 Q2W (1 [REDACTED] and 7 maintenance doses), or placebo to match TEV-48574, in a 1:1 ratio, given sc via the KORU FreedomEdge® syringe infusion system Q2W over a 16-week treatment period for a total of 8 doses.

A pre-specified interim futility analysis was conducted on 64 patients. Teva determined that the primary endpoint result, reduction in LoAC, met the decision rule for futility, meaning that the likelihood of a positive outcome of the completion of the study was small. Based on the results of the primary endpoint futility analysis, Teva decided to stop the study on 22 December 2021.

A total of 65 patients were randomized into the study; 1 patient did not receive investigational medicinal product (IMP). No deaths occurred. Two treatment-emergent serious adverse events were reported; neither were assessed as related to the IMP by the investigator and sponsor. There were 28 patients who withdrew from the study due to LoAC. There were no early terminations due to adverse events.

2.3. Known and Potential Benefits and Risks to Patients

2.3.1. Known and Potential Benefits and Risks of the Test Investigational Medicinal Product(s)

Given the targeted action of TEV-48574 on TL1A, and considering that the product is a mAb, immunosuppression (eg, higher risk for infections and malignancies or incomplete response to vaccines), systemic hypersensitivity, and immunogenicity may be considered potential risks of TEV-48574. None of these risks were observed in either portion of Study TV48574-SAD-10126, except for immunogenicity, predominantly in the low-dose level cohorts up to and including 200 mg in single and repeat-dose settings. However, the observed immunogenicity was not

associated with safety signals; a single patient with decreased serum concentration of TEV-48574 associated temporally with a treatment-emergent ADA response in the MAD portion of the study in the 200 mg cohort.

Transient, mostly mild injection site findings were evident in subjects/patients treated with TEV-48574. No risk was identified that would impact the safety of patients enrolled in clinical studies.

The anti-TL1A activity of TEV-48574 may have an anti-inflammatory and anti-fibrotic effect in patients with IBD, leading to improvement of their disease conditions (see Section 2.1).

In summary, the benefit and risk assessment for TEV-48574 is favorable following review of the outlined data.

Additional information regarding benefits and risks to patients may be found in the IB.

2.3.2. Overall Benefit and Risk Assessment for This Study

This study will investigate the pharmacokinetics, efficacy, safety, and tolerability of TEV-48574 in adult patients with IBD (UC or CD). As described in Section 2.1, such patients may benefit from the development of further therapy options.

Based on the mechanism of action of TEV-48574 and that the exposure in patients with IBD is expected to be similar to the exposure demonstrated in HV and patients with asthma, the safety profile in the IBD population is expected to be comparable with that established in HV and patients with asthma.

Management of the patients' safety during the study that is expected to mitigate risk is detailed in Section 4 (investigational plan) and Section 8 (safety measurements and assessments); also refer to Section 10.13 for a description of the futility analysis, which will determine if recruitment should be stopped due to futility.

In addition to the monitoring of individual patients, an Independent Data Monitoring Committee (IDMC), as described in Section 6.9.3, will review accumulating unblinded safety data.

Overall, the risks for patients in this study are mitigated comprehensively and are considered adequate to justify the study.

3. STUDY OBJECTIVES, ENDPOINTS, AND ESTIMANDS

3.1. Primary and Secondary Study Objectives and Endpoints

The primary and secondary study objectives and endpoints are:

Objectives	Endpoints

The primary objective of the study is to characterize the efficacy of TEV-48574 sc administered Q2W in adult patients with IBD (moderate to severe UC or CD), as assessed by induction of clinical remission (UC) and endoscopic response (CD) at week 14.
	
The primary efficacy endpoint is response (yes or no) at week 14, where response in UC patients is defined as clinical remission and response in CD patients is defined as endoscopic response. Clinical remission and endoscopic response are determined as follows:
 
 • Clinical remission at week 14 in patients with moderate to severe UC. Clinical remission is a modified (9-point rectal bleeding, stool frequency, and endoscopy) Mayo score of ≤ 2 points, which is defined by: 
 ◦ stool frequency subscore of 0 or 1, ◦ rectal bleeding subscore of 0, and ◦ endoscopic subscore of 0 or 1, where a score of 1 does not include “ friability ” • Endoscopic response at week 14 in patients with moderate to severe CD, defined as a reduction in Simple Endoscopic Score for Crohn’s Disease (SES-CD) of at least 50% from baseline

A secondary objective of the study is to evaluate the efficacy of 2 different doses of TEV-48574 sc administered Q2W in adult patients with IBD (moderate to severe UC or CD) as assessed by multiple standard measures at week 14.
	
The secondary efficacy endpoints to be measured in patients with moderate to severe UC are as follows:
 
 • Clinical response at week 14, defined as a decrease from baseline in the modified (9-point rectal bleeding, stool frequency, and endoscopy) Mayo score of at least 2 points AND at least a 30% reduction from baseline with either a decrease in rectal bleeding subscore of at least 1 or an absolute rectal bleeding subscore of less than or equal to 1 • Endoscopic improvement defined as a Mayo endoscopic subscore of 0 or 1 at week 14 • Endoscopic remission defined as a Mayo endoscopic subscore of 0 at week 14 • Clinical response defined as decrease from baseline of at least 50% in 2-item patient-reported outcome (PRO2; rectal bleeding and stool frequency) at week 14 • Clinical remission defined as score of rectal bleeding = 0 and stool frequency = 0 on the PRO2 scale at week 14 
The secondary efficacy endpoints to be measured in patients with moderate to severe CD are as follows:
 
 • Clinical response defined as a ≥ 100-point decrease in Crohn’s Disease Activity Index (CDAI) score from baseline at weeks 4, 8, 12 and 14 • Clinical remission defined as a CDAI score < 150 at week 14 • Clinical response defined as a decrease from baseline of at least 50% in PRO2 (PRO2 is defined as having 2 components, abdominal pain and stool frequency) at week 14

Objectives	Endpoints
	
 • Clinical remission defined as abdominal pain ≤ 1 and stool frequency ≤ 3 on the PRO2 scale at week 14 • Endoscopic response defined as a decrease in modified multiplier (MM)-SES-CD of $>50\%$ from baseline at week 14

A secondary objective of the study is to evaluate the safety and tolerability of 2 different doses of TEV-48574 sc administered Q2W in adult patients with IBD (moderate to severe UC or CD).
	
The safety and tolerability measures/parameters are as follows:
 
 • Adverse events • Change from baseline in clinical laboratory test results (serum chemistry, hematology, and urinalysis) • Change from baseline in vital signs measurements (blood pressure, pulse rate, body temperature, and respiratory rate) • Change from baseline in 12-lead electrocardiogram findings • Patients who stopped the investigational medicinal product due to adverse events • Local tolerability at the injection site

A secondary objective of the study is to evaluate the immunogenicity of 2 different doses of TEV-48574 sc administered Q2W in adult patients with IBD (moderate to severe UC or CD).
	
The immunogenicity endpoints for this study are as follows:
 
 • Change from baseline in treatment-emergent anti-drug antibody (ADA) at weeks 2, 4, 8, 14, and follow-up visit • Presence of neutralizing ADA in ADA positive patients at weeks 2, 4, 8, 14, and follow-up visit

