5.1. Patient Inclusion Criteria

Patients may be randomized/enrolled in this study only if they meet all of the following criteria:

- a. Adults of male and female sex (without restrictions on gender) between 18 and 75 years of age, inclusive, at the time of informed consent.
- b. Diagnosis of UC or CD for ≥ 3 months.
- c. UC patients only: Patient with moderate to severe active UC as defined by the 3-component modified Mayo score of 5 to 9, inclusive, with an endoscopic subscore of ≥ 2 (from central reading).
- d. CD patients only: Patient with moderate to severe active CD as determined by a CDAI score of ≥ 220 and ≤ 450 .
- e. CD patients only: SES-CD score of ≥ 6 (≥ 4 for isolated ileal disease).
- f. UC patients only: Active disease beyond the rectum (>15 cm of active disease at the screening endoscopy [sigmoidoscopy]).
- g. Patient must have inadequate response to, loss of response to, or intolerance to:
 - At least 1 of the following therapies: corticosteroids, immunosuppressants, or an approved advanced therapy for IBD including biologics (anti-TNF, anti-integrins, anti-IL-12/23, or anti-IL-23), JAK inhibitors, or S1P receptor modulators. No more than 3 locally approved classes of biologics.
 - Inadequate response to, loss of response to, or intolerance to corticosteroid treatment is defined as 1 or more of the following:
 - Steroid refractory: persistent symptoms of active disease despite treatment with at least one 4-week induction regimen that included a dose of ≥ 30 mg prednisone (oral) daily for at least 2 weeks or intravenous (iv) for at least 1 week within the previous 5 years;
 - Steroid dependent: 2 failed attempts to taper steroids below a dose equivalent to 10 mg prednisone (oral) daily within the previous year;
 - Steroid intolerant: history of intolerance to corticosteroids (including, but not limited to, Cushing's syndrome, osteopenia/osteoporosis, hyperglycemia, insomnia, and infection) within the previous 5 years.
 - Inadequate response to, loss of response to, or intolerance to prior immunosuppressant treatment is defined by 1 or more of the following:

- Persistent signs and symptoms of active disease despite a history of at least 1 regimen of oral AZA or 6-MP and/or methotrexate consistent with the regional standard of care;

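### Crohn's disease PRO2 remission has no baseline condition and can already be met at entry, and its stool threshold does not fit the stated 0-3 stool scale

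*Protocol*

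**What the plan says.** For CD, Protocol Section 3.1 sets two response and two remission endpoints on symptom indices.

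- CDAI response: "Clinical response defined as a ≥ 100-point decrease in" the index.
- CDAI remission: "Clinical remission defined as a CDAI score < 150 at week 14".
- PRO2 response: "Clinical response defined as a decrease from baseline of at least 50% in PRO2 (PRO2 is defined as having 2 components" (the items are stool frequency and abdominal pain).
- PRO2 remission: "Clinical remission defined as abdominal pain ≤ 1 and stool frequency ≤ 3 on the PRO2 scale at week 14".

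The response endpoints are changes from baseline and the remission endpoints are absolute states. Section 3.3 repeats both PRO2 definitions as exploratory endpoints at weeks 2, 4, 6, 8, 10 and 12.

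Entry in Section 5.1 is by total index, "as determined by a CDAI score of ≥ 220 and ≤ 450", together with a minimum SES-CD of 6 (4 for isolated ileal disease). No minimum is set for abdominal pain or stool frequency.

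Section 7.1.4 describes CD PRO2 as a sum of two items taken from the CDAI, each scored 0 to 3. Section 7.1.3 gives the CDAI stool item as a daily count of liquid or soft stools summed over 7 days.

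Section 10.5.4.4 analyses each binary secondary endpoint by its own logistic regression, with the respective baseline measurement as a covariate. Section 10.5.4 uses the mITT set for all efficacy analyses.

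**The concern.** A remission endpoint in an induction trial should count patients who moved into remission. If the state can be met on entry, some week-14 remitters will be patients in whom nothing happened. Randomisation spreads them evenly in expectation, so they create no false effect. They do raise the rate in every arm and pull the difference towards zero.

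The second problem is that the endpoint cannot be read one way from the text. If stool frequency runs from 0 to 3, the condition of at most 3 is always true and remission reduces to abdominal pain of at most 1. If it is a daily count, Section 7.1.4 states the wrong range. The choice changes who is a remitter and also changes the sum used for the 50% response.

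The ulcerative colitis (UC) endpoints in the same section do not have this property. UC entry needs a modified Mayo score of at least 5 and remission a score of at most 2, a fall of at least 3 points and at least 3/5 = 60%. With an endoscopic subscore of at most 3, bleeding plus stool frequency is at least 5 - 3 = 2 at entry, so UC PRO2 remission (0 and 0) cannot be met at baseline.

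**Working it through.** The protocol states no figure on this point, so there is none to reproduce. The checks use only its definitions, except where an assumption is named.

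**1. Can an eligible patient already be in PRO2 remission? (stool frequency read as a daily count)**

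Weights are from Section 7.1.3. I assume constant daily values, with the PRO2 baseline reflecting the same week as the CDAI.

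- Stools: 3 × 7 × 2 = 42
- Abdominal pain: 1 × 7 × 5 = 35
- Well-being: 3 × 7 × 7 = 147
- Total: 42 + 35 + 147 = 224, which is at least 220

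A second route has milder well-being: 42 + 35 + (2 × 7 × 7 = 98) + one complication (20) + antidiarrhoeal use (30) = 225. Both patients satisfy the CDAI criterion and have pain of at most 1 and stools of at most 3.

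**2. The same question on the 0-3 scale of Section 7.1.4**

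All 4 possible stool grades are at most 3, so the stool condition excludes no one. Remission becomes pain of 0 or 1, whatever the stool grade. Of the 4 × 4 = 16 possible baseline states, 2 × 4 = 8 already qualify. These are counts of states, not proportions of patients.

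**3. Size of the dilution**

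Let a fraction f of each arm be in PRO2 remission at baseline and remain there, and let D be the difference among the others. The observed difference is (1 - f) × D. If the placebo rate among the others is p, the observed placebo rate is f + (1 - f) × p. The protocol gives neither f nor D. With D = 20 points and p = 12% taken for illustration:

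| f (assumed) | Difference | Placebo rate |
|---|---|---|
| 5% | 0.95 × 20 = 19 points | 0.05 + 0.95 × 0.12 = 16.4% |
| 10% | 0.90 × 20 = 18 points | 0.10 + 0.90 × 0.12 = 20.8% |
| 20% | 0.80 × 20 = 16 points | 0.20 + 0.80 × 0.12 = 29.6% |

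**4. PRO2 remission without PRO2 response**

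On the 0-3 scale, pain 3 and stool 3 (sum 6) falling to pain 1 and stool 3 (sum 4) is remission with a fall of 2/6 = 33%, short of 50%.

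**5. CDAI remission without CDAI response (lesser point)**

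The highest integer score in remission is 149.

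- From 220: 220 - 149 = 71
- From 248: 248 - 149 = 99
- From 249: 249 - 149 = 100

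So a remitter can be a non-responder only from baselines 220 to 248, which is 29 of the 231 eligible integer values. For an expected frequency I assume baseline CDAI normal with mean 300 and SD 50, truncated to 220-450, and a fall with mean 60 to 130 and SD 85. About 10% of patients then start at 220-248, and about 0.6% of all CD patients are remitters but non-responders. That is 0.006 × 120 = 0.7 of a patient, or 0.24 per arm of 40. Varying the baseline mean over 290-310 and the SD over 45-55 gives 0.3% to 0.9%, or about 0.4 to 1.1 patients in 120.

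**The case against.** The strongest reply is that nothing here is contradictory. Response is a change and remission is a state. Both can be computed, a patient can meet both, and the protocol never says that remission must lie within response. Each endpoint has its own model with a nominal p-value, and Section 10.6 makes no multiplicity adjustment. That stands. A reader might infer from the overlap that the paired CD endpoints contradict each other; the documents support only that they are not nested.

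It can also be said that unchanged baseline remitters fall equally in randomised arms and cause no bias under the null, that their share is unknown, and that the model adjusts for baseline. The first two are right and limit the size of the point. The third helps less than it seems. The covariate accounts for baseline severity, but an unchanged patient is still a remitter at week 14, and the reported difference in proportions still averages over such patients.

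A further tempting illustration is a fall from 5 stools and pain 2 to 3 stools and pain 1, a remission with a 3/7 = 43% fall. It holds only on the daily-count reading; a stool value of 5 does not exist on the 0-3 scale that Section 7.1.4 states.

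**Conclusion.** The point holds for CD PRO2 remission. The definition has no baseline condition and entry sets no pain or stool minimum, so an eligible patient can count as a week-14 remitter without any change. This is true on either reading of the stool item. The stool threshold in Section 3.1, the daily count in Section 7.1.3 and the 0-3 scale in Section 7.1.4 do not fit together and must be reconciled.

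The size cannot be fixed from the protocol. It rests on an assumed share of baseline remitters: 5% costs 1 point of a 20-point difference and 20% costs 4 points. The daily-count example needs poor well-being, or complications and antidiarrhoeals, alongside mild pain and few stools. That is possible, but its frequency is unknown. On the 0-3 reading the exposure is wider, because only pain matters.

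The CDAI gap is real but expected to affect about one patient or fewer in 120 under the assumptions shown, and would not justify a change by itself. Only secondary and exploratory endpoints are touched. The CD primary endpoint (SES-CD), the sample size and the success rule are not affected.

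**What to change.** First, reconcile Sections 3.1, 7.1.3 and 7.1.4: state whether CD PRO2 stool frequency is a daily count or a 0-3 grade, and make the remission threshold and the sum used for the 50% response consistent with it.

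Then, in Section 3.1 and for the Section 3.3 visits, analyse CD PRO2 remission in mITT patients who do not meet the definition at baseline, and show the full-mITT result alongside. The subset is defined before treatment, so the randomised comparison is kept.

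Optionally, define CDAI response as a fall of at least 100 points or a CDAI below 150, which closes the 220-248 gap.

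PRO2 response should not be widened to include PRO2 remission unless baseline remitters are removed from that endpoint too. Otherwise unchanged patients would become automatic responders, which the present 50% rule prevents for any non-zero baseline.

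The cost is endpoint wording and derivation code, one extra table per visit, and the loss of baseline remitters, probably few, from one denominator. With the optional change, CDAI response rates would rise very slightly in all arms.
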